4.6.2 Duration of Follow Up

Once patients are off treatment for any reason, they will have a final off-treatment visit approximately 30 days post-last dose of study therapy. Thereafter, they will be followed with at least one clinic visit every 3 months for up to 2 years from end of treatment. Patients removed from treatment for unacceptable adverse events will be followed until resolution or stabilization of the adverse event.

For patients who undergo allogeneic stem cell transplant (SCT) within 2 years of study treatment, transplant parameters and adverse events will be recorded as detailed in section 4.6.3.

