4.6.3 Subject Withdrawal/Discontinuation Criteria from Treatment and/or Overall Study

Subjects may withdraw consent at any time for any reason or be dropped from the trial at the discretion of the investigator should any untoward effect occur. In addition, a subject may be withdrawn if enrollment into the trial is inappropriate, the trial plan is violated, or for administrative and/or other safety reasons. Specific details regarding discontinuation or withdrawal are provided in Table 4.1.

A subject must be discontinued from the trial for any of the following reasons:

- Patient voluntarily withdraws from treatment (follow-up permitted)
- The subject or legal representative (such as a parent or legal guardian) withdraws consent (no follow-up permitted).
- Confirmed radiographic disease progression
- Note: For unconfirmed radiographic disease progression, please see Section 5.1.6
- Unacceptable toxicity/adverse experiences as described in Section 4.4
- Intercurrent illness that prevents further administration of treatment
- Investigator's decision to withdraw the subject (i.e. continuation not in the patient's best interest)
- The subject has a confirmed positive serum pregnancy test
- Patient develops a second malignancy that requires treatment which would interfere with this study
- Noncompliance or inability to comply with trial treatment or procedure requirements
- The subject is lost to follow-up
- Administrative reasons

The End of Treatment and Follow-up visit procedures are listed in Section 5 (Protocol Flow Chart). After the end of treatment, each subject will be followed for 30 days for adverse event monitoring (serious adverse events will be collected for 90 days after the end of treatment as. Subjects who discontinue for reasons other than progressive disease will have post-treatment follow-up for disease status until disease progression, initiating a non-study cancer treatment, withdrawing consent or becoming lost to follow-up. After documented disease progression each subject will be followed by telephone for overall survival until death, withdrawal of consent, or the end of the study, whichever occurs first.

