- ¹⁴ PET/CT is required for eligibility within 6 weeks prior to registration (standard of care) and at specified time points for tumor assessment for the primary endpoint analysis. PET#2 should take place prior to starting AVD (research procedure). PET#3 should take place at the end of AVD Cycle 2 (standard of care). Copies of PET/CT scans should be de-identified and CD disks with DICOM files shipped within 30 days for central review as outlined in section 6.3.1.
- ¹⁵ All patients will have a PET/CT 2-6 weeks after the completion of chemotherapy (or diagnostic CT's for patients with Stage I/II disease and a negative PET#3) (standard of care). This will be prior to starting consolidation treatment (when applicable) or as part of the procedures for study discontinuation. Patients receiving consolidation will also have a final PET/CT as part of study discontinuation.
- ¹⁶ For patients who receive pembrolizumab consolidation, imaging is recommended every 3 months. Once a PET-CT is negative, patients may undergo CT's every three months during consolidation.
- ¹⁷ Diagnostic quality CT scan of the chest/abdomen/pelvis is required within 6 weeks prior to registration. If there is involvement of the neck then a diagnostic quality CT Neck is required.
- ¹⁸ Correlative studies on tissue specimens are recommended if there is adequate tissue on the baseline sample acquired for diagnosis. Patients who agree to undergo a repeat biopsy (optional: done as a research procedure) for the interim assessment will provide tissue 2-4 weeks after the first dose of pembrolizumab as specified in the lab manual, however repeat biopsy is not required.
- ¹⁹ See separate lab manual for details of correlative studies (research procedures). Study labs include:
 - (1) sodium heparin tube for FlowCore,
 - (2) SST tube for Inflammatory and Immune Markers,
 - (3) SST tube for Soluble PD-L1
 - (4) SST for CCL17

¹ Treatment cycle of pembrolizumab defined as 21 days, Treatment cycle of AVD defined as 28 days with treatment on days 1 and 15

² Interim assessment by FDG-PET #2 for primary endpoint assessment on day 64 +/- 3 days

³Labs including CBC w/ANC and comprehensive chemistry panel, physician visit with physical examination and vital signs to be performed on day 1 of each cycle of AVD.

⁴ Interim assessment by FDG-PET #3 for PET-directed therapy on day 117-120 prior to AVD cycle 3

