⁵ Elderly patients may receive consolidation for a total of up to 1 or 2 years pembrolizumab treatment. Elderly patients who do not achieve CR after additional AVD will have pembrolizumab consolidation for up to 32 additional doses. Elderly patients with Stage III/IV disease who achieve CR after <6 cycles AVD will receive pembrolizumab consolidation for up to 14 additional doses. See section 4.2.3 for details.

⁶ See study schema in 1.2

⁷ Patients will be followed (either by routine clinic visit or by phone call) for survival every 12 weeks (±7 days) for 2 years from the last dose of study drug. Patients should also be monitored for occurrence of an allogeneic stem cell transplant within 24 months from the last study treatment. If patient undergoes an allo-SCT in this timeframe, transplant parameters and adverse events must be reported as specified in section 4.6.3 (up to 18 months from the time of SCT).

⁸ Vital Signs include: Blood pressure, pulse, respiratory rate, and oxygen saturation

⁹ See Appendix A

¹⁰ See Appendix D

¹¹ Comprehensive chemistry panel and CBC with differential are required within 14 days of study registration. Chemistry panel will include glucose, calcium, albumin, ALT, AST, sodium, potassium, total bilirubin, alk phose, and creatinine. CBC with differential must include Absolute Neutrophil Count.

¹² At baseline and every 6 weeks while on therapy with pembrolizumab.

¹³Patients must have HIV Ab screen; and Hepatitis B Sag, Sab, and core; and Hepatitis C Ab testing within 6 weeks of registration.

Trial Period:	Screening Phase	Treatment Cycles ¹						Off Rx	Surveillance			
		Pemb	orolizun	nab		AVD ^{2,3}		AVD ^{3,4}	sment	Pembrolizumab ⁵	Discont	Survival Follow-Up
Treatment Cycle/Title:	Main Study Screening	1	2	3	PET #2	1-2	PET #3	3-66	emo Asses	4-35		
Scheduling Window (Days):	Within 28 days of registration	1 ± 3	22 ± 3	43 ± 3	[64 ± 3	[120 ± 3	Post-Che	2-4 weeks after last dose of chemotherapy ± 3	30 days after last dose (pembro or AVD, ±5 days)	Every 12 weeks

²⁰ Adverse events will be followed for the first 30 days after treatment discontinuation. SAE's will be recorded for 90 days after treatment discontinuation. For patients who undergo allogeneic stem cell transplant (SCT) within 24 months of last study treatment, transplant parameters and adverse events will be recorded according to section 4.6.3 (up to 18 months from the time of SCT).

²¹ Echo or MUGA to be repeated after 4 cycles of doxorubicin

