6.4.4 Progression Free Survival (PFS)

PFS will be defined as the length of time from treatment on protocol until the first occurrence of disease relapse, progression, re-initiation of cytotoxic chemotherapy, or death due to disease, or until last contact if the patient did not experience any of these from the end of treatment through two years of follow up.

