10.3.2 Analytic Plan for Secondary Objectives

To assess safety and tolerability, all adverse events will be summarized in terms of type, grade, timing and attribution to treatment. All enrolled patients who receive at least one injection of study drug or undergo a study-related procedure will be included in the safety analysis. The highest toxicity grades per patient will be tabulated for AEs and laboratory measurements, and the number and percent of patients reporting AEs will be quantified. Listings will be required for all on-study deaths, SAEs and AEs that lead to withdrawal from study. Narratives for all SAEs and deaths on-study will be required. These summaries will be done by age cohort.

Continuous toxicity monitoring will occur using the method of Ivanova et al.⁵¹ While this method may be used to identify an unacceptable level of toxicity after each patient, only values for every 5 patients will be given here. The following table gives the number of unacceptable toxicities that need to be observed after 5, 10, 15, 20, 25, 30 patients to identify an adverse toxicity rate exceeding 20% with a false positive rate (after each patient) of 2% and a desired probability of early stopping of 5%. Unacceptable toxicity is defined as any toxicity requiring discontinuation of pembrolizumab, as defined in Table 4.1.

Number of patients observed: 5 10 15 20 25 30 Number of observed toxicities: 4 6 8 9 11 12

Response assessment: Anti-tumor activity will be assessed using the LUGANO 2014 Response Criteria (Appendix C). Patients who receive consolidation with pembrolizumab will also have disease assessed by the Immune Response Criteria (Appendix F) as an exploratory assessment. To assess progression free survival

(PFS) and overall survival (OS), Kaplan Meier curves for progression and survival will be calculated for each cohort. The 3-year PFS will be determined from this curve for all patients

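### PFS is censored at last contact, which may be a survival phone call, so time without a disease assessment can count as progression-free and PFS may read too high

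*Combined protocol and SAP*

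**What the plan says.** - **Censoring rule.** Section 6.4.4 ends PFS for a patient without an event at last contact: "or until last contact if the patient did not experience any of these from the end of treatment through two years of follow up". Section 6.4.5 uses the same rule for OS.
- **Analysis.** Section 10.3.2 adds no censoring rule. It says only that "Kaplan Meier curves for progression and survival will be calculated for each cohort", and that a 3-year PFS will be read from the curve for all patients.
- **Follow-up in the schedule.** Footnote 7 of Section 5.0 reads: "Patients will be followed (either by routine clinic visit or by phone call) for survival every 12 weeks (±7 days) for 2 years". The Survival Follow-Up column marks post-study anticancer therapy status, survival status and adverse event review. It marks no PET-CT, CT or physical examination.
- **Follow-up in the body text.** Section 4.6.2 says of patients off treatment that "they will be followed with at least one clinic visit every 3 months for up to 2 years from end of treatment". Section 4.6.3 says that patients who stop for reasons other than progression "will have post-treatment follow-up for disease status until disease progression, initiating a non-study cancer treatment, withdrawing consent or becoming lost to follow-up". It places telephone follow-up later: "After documented disease progression each subject will be followed by telephone for overall survival until death".
- **Last scheduled imaging.** Without consolidation, this is the scan 2-6 weeks after chemotherapy or at discontinuation. With consolidation, scans are recommended every 3 months during it, and footnote 15 adds: "Patients receiving consolidation will also have a final PET/CT as part of study discontinuation".

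**The concern.** A survival call establishes that a patient is alive. It does not establish that the disease has not come back. Response and progression are judged by the Lugano 2014 criteria, and relapse in Section 6.4.3 by node size, new lesions or biopsy, none of which can be read over the telephone. Last contact is therefore a sound censoring date for OS but not for PFS. A patient whose assessments stop while calls continue stays in the PFS risk set as progression-free, adding to the denominator without being able to contribute an event found on assessment. If a progression in that interval goes unreported, the curve is too high from then on. What is at stake is the planned Kaplan-Meier PFS and the 3-year figure read from it.

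**Working it through.** The plan gives no sample size, power or expected rate for PFS, so there is no figure of its own to reproduce. The check has three steps.

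**1. The passages side by side.**

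| Question | 5.0, footnote 7 and Survival Follow-Up column | 4.6.2 and 4.6.3 |
|---|---|---|
| Form of contact | Clinic visit or phone call | Clinic visit; telephone only after progression |
| Purpose | Survival (therapy status and AEs also marked) | Disease status until progression |
| Interval | 12 weeks | 3 months (4.6.2); none given (4.6.3) |
| Imaging or examination | None marked | No method stated |
| Effect on PFS censoring date | None | None |

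Under the left column, contact without assessment is permitted. Under the right column it is not intended, but a patient who misses visits and answers the phone is still censored at the call, because 6.4.4 governs the date.

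**2. A simple bound on size.** Suppose k of 26 patients are event-free at the start of follow-up and then have contact but no assessment for 24 months, with no relapse reported. Let q be the 24-month event risk. PFS is then overstated by at most about q × k/26; the exact value is this multiplied by PFS at the start of the window, which is below 1. Inputs: 5-year PFS of 75-80% overall and 5-year RFS of 30-50% in the elderly (both Section 1.1); k = 3 to 8 is an assumption; 26 is the evaluable target. Under constant hazard, q = 1 − S₅^(24/60).

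| 5-year rate | q | k = 3 | k = 8 |
|---|---|---|---|
| 80% | 1 − 0.80^0.4 = 8.5% | 1.0 points | 2.6 points |
| 75% | 1 − 0.75^0.4 = 10.9% | 1.3 points | 3.3 points |
| 50% (elderly) | 1 − 0.50^0.4 = 24.2% | 2.8 points | 7.4 points |
| 30% (elderly) | 1 − 0.30^0.4 = 38.2% | 4.4 points | 11.8 points |

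The overall rates give about 1.0 to 3.3 points (3.4 if q is rounded to 11%). The elderly rows would apply only if all 26 patients carried that risk, which they do not. With 30 patients as denominator, every figure shrinks by 26/30.

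**3. A simulation that lets some relapses be learned by phone.** Assumptions: exponential progression; 3-monthly assessments; a share f of patients whose assessments stop at a random visit from month 6 while contact continues; probability d that a later progression is learned at the contact. PFS is read at month 30, about 6 months of treatment plus 24 of follow-up.

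| 5-year rate | True PFS | f = 20%, d = 0.5 | f = 20%, d = 0 | f = 50%, d = 0 |
|---|---|---|---|---|
| 77.5% (midpoint, overall) | 88.0% | 88.5% | 89.1% | 90.7% |
| 40% (midpoint, elderly) | 63.2% | 64.7% | 66.2% | 70.7% |

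The last three columns use last-contact censoring. Across f = 10-50% and d = 0-0.8 the upward shift is about 0.1 to 2.7 points at the overall rate and 0.3 to 7.5 at the elderly rate. At d = 1 it is zero apart from simulation noise. Censoring at the last assessment recovers the true value in this model, where assessments stop for reasons unrelated to the disease.

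**The case against.** The strongest reply is that the body text already covers the patients concerned. Only patients without progression can be censored for PFS, and for them 4.6.2 gives clinic visits and 4.6.3 gives disease-status follow-up, with the telephone reserved for after progression. A reader of footnote 7 alone might infer that event-free patients are followed for two years by phone only. The documents do not support that: it requires the footnote to override both sections. What remains is an unresolved conflict, and a censoring date that neither section changes.

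Second, the contact is not blind to progression. Post-study anticancer therapy status is collected, footnote 7 asks about allogeneic transplant, and 6.4.4 counts restarting cytotoxic chemotherapy as a PFS event. Some relapses will therefore be learned by phone, so the curve may be too high but is not certain to be. This stands.

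Third, a reader might assume a 20-30% event risk over follow-up and reach 0.30 × 8/26 = 9.2 points for the whole cohort. That risk roughly matches only the elderly RFS; the overall PFS gives 8.5-10.9% over 24 months.

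Fourth, a reader might infer that patients without consolidation are more exposed throughout. After treatment ends the window is up to 24 months in both groups, and no imaging is marked for either. A difference arises only at times that fall within consolidation.

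**Conclusion.** The point holds as a defect in the definition of PFS. As written, time with contact but no disease assessment is credited as progression-free. Last-contact censoring does not lower expected PFS, and it raises it when a progression after the last assessment goes unlearned. Whether this happens often depends on which follow-up passage the sites follow and on how many relapses are reported at the contact. The documents settle neither, so the size is illustrative: about 1.0 to 3.3 points at the overall 5-year PFS under constant hazard, with 3 to 8 of 26 patients unassessed for 24 months and no relapse reported; larger at the elderly rates; small if 3-monthly visits with recorded disease status take place; zero if every progression is learned. PFS carries no threshold or test in this plan, and the primary CR endpoint at PET#2 is untouched. The change should be made, but it does not put the trial's main conclusion in doubt.

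**What to change.** - **Section 6.4.4.** Censor patients without a PFS event at the date of the last disease assessment showing no relapse or progression, where an assessment is imaging or a clinic visit with documented disease status. Keep last contact for OS in 6.4.5 only.
- **Section 10.3.2.** State the same rule and report last-contact censoring as a sensitivity analysis.
- **Follow-up passages.** Reconcile footnote 7 and the Survival Follow-Up column with 4.6.2 and 4.6.3, so that disease status is recorded at the follow-up visits already planned, and say which records count as an assessment for PFS.

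**Cost.** One sentence in 6.4.4, one in 10.3.2, and an aligned footnote. The price is shorter PFS follow-up and wider intervals. This could be marked if disease status is not recorded at the visits, because many patients would then be censored near the end of treatment. The 3-year figure is the most exposed. For AVD patients without consolidation, the Study Summary durations give 9 + 16 to 24 weeks of treatment plus 104 weeks of follow-up, or 129 to 137 weeks, already short of 156. If later scans are prompted mainly by symptoms, censoring well patients at an old scan can bias PFS downward. That is why clinic visits with recorded disease status should count, and why both censoring rules should be reported.

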6.4.5 Overall Survival (OS)

OS will be defined as time from study enrollment until death, or until last contact if the patient did not die from the end of treatment through two years of follow up.

7.0 ADVERSE EVENTS

This study will be conducted in compliance with the Data Safety Monitoring Plan (DSMP) of the Robert H. Lurie Comprehensive Cancer Center of Northwestern University (please refer to Appendices for additional information). The level of risk attributed to this study requires a high level of monitoring, as outlined in the DSMP. In addition, the study will abide by all safety reporting regulations, as set forth in the Code of Federal Regulations and as required by the NCI AdEERS Reporting Guidelines.

7.1 Adverse Event Monitoring

Adverse event data collection and reporting, which are required as part of every clinical trial, are done to ensure the safety of subjects enrolled in the studies as well as those who will enroll in future studies using similar agents. Adverse events are reported in a routine manner at scheduled times during a trial (see Section 5 for timepoints). In addition, certain adverse events must be reported in an expedited manner to allow for optimal monitoring and patient safety and care.

All patients experiencing an adverse event, regardless of its relationship to study drug, will be followed until:

- the adverse event resolves or the symptoms or signs that constitute the adverse event return to baseline;
- any abnormal laboratory values have returned to baseline;
- there is a satisfactory explanation other than the study drug for the changes observed; or
- death.

Initial Version date: March 10th, 2017

7.2 Definitions & Descriptions

7.2.1 Adverse Event

An adverse event (AE) is any untoward medical occurrence in a patient receiving study treatment and which does not necessarily have a causal relationship with this treatment. An AE can therefore be any unfavorable and unintended sign (including an abnormal laboratory finding), symptom, or disease temporally associated with the use of an experimental intervention, whether or not related to the intervention.

Any worsening (i.e., any clinically significant adverse change in frequency and/or intensity) of a preexisting condition that is temporally associated with the use of the Merck's product, is also an adverse event.

Changes resulting from normal growth and development that do not vary significantly in frequency or severity from expected levels are not to be considered adverse events. Examples of this may include, but are not limited to, teething, typical crying in infants and children and onset of menses or menopause occurring at a physiologically appropriate time.

Merck product includes any pharmaceutical product, biological product, device, diagnostic agent or protocol-specified procedure, whether investigational (including placebo or active comparator medication) or marketed, manufactured by, licensed by, provided by or distributed by Merck for human use.

Adverse events may occur during the course of the use of Merck product in clinical trials, or as prescribed in clinical practice, from overdose (whether accidental or intentional), from abuse and from withdrawal.

Progression of the cancer under study is not considered an adverse event.

All adverse events that occur after the consent form is signed but before treatment allocation/randomization must be reported by the investigator if they cause the subject to be excluded from the trial, or are the result of a protocol-specified intervention, including but not limited to washout or discontinuation of usual therapy, diet, placebo treatment or a procedure.

From the time of treatment allocation/randomization through 30 days following cessation of treatment, all adverse events must be reported by the investigator. Such events will be recorded at each examination on the Adverse Event eCRFs. The reporting timeframe for adverse events meeting any serious criteria is described in section 7.3. The investigator will make every attempt to follow all subjects with non-serious adverse events for outcome.

Recording of AEs should be done in a concise manner using standard, acceptable medical terms. In general, AEs are not procedures or measurements, but should reflect the reason for the procedure or the diagnosis based on the abnormal measurement. Preexisting conditions that worsen in severity or frequency during the study should also be recorded (a preexisting condition that does not worsen is not an AE). Further, a procedure or surgery is not an AE; rather, the event leading to the procedure or surgery is considered an AE.

If a specific medical diagnosis has been made, that diagnosis or syndrome should be recorded as the AE whenever possible. However, a complete description of the signs, symptoms and investigations which led to the diagnosis should be provided. For example, if clinically significant elevations of liver function tests are known to be secondary to hepatitis, "hepatitis" and not "elevated liver function tests" should be recorded. If the cause is not known, the abnormal test or finding should be recorded as an AE, using appropriate medical terminology (e/g/ thrombocytopenia, peripheral edema, QT prolongation).

